12.2.7. Overdose of TVB-2640

Signs and symptoms of an overdose should be reported as AEs. Overdoses will not be considered SAEs unless the outcome of the overdose meets seriousness criteria (see Section [12.2.1.2](#)).

12.2.8. Protocol Deviations Due to an Emergency or Adverse Event

Departures from the protocol will be determined as allowable on a case-by-case basis and only in the event of an emergency. The Investigator or other physician in attendance in such an emergency must contact the Medical Monitor as soon as possible to discuss the circumstances of the emergency.

The CRO's Medical Monitor, in conjunction with the Investigator, will decide whether the subject should continue to participate in the study. All protocol deviations and reasons for such deviations must be documented in the subject's source records.

13. STATISTICAL CONSIDERATIONS

13.1. Statistical General Considerations

This is a multi-center, randomized, double-blind, placebo-controlled, parallel-design study to evaluate the safety and efficacy of TVB-2640 compared with matching placebo in subjects with NASH.

For “change from Baseline” and “percent change from Baseline” calculations, “Baseline” refers to the last measurement obtained prior to the first administration of study drug. Study Day 1 is the first day of study treatment (TVB-2640 50 mg or placebo). Demographic data (including age, race, ethnicity, sex, height, and weight), medical history, prior treatments, pretreatment clinical characteristics, and other baseline characteristics will be summarized by treatment group and overall.

Descriptive statistics will be displayed by treatment group for all subjects with liver fibrosis stage F2-F3, for all subjects with liver fibrosis stage F1-F3, and for all subjects, as appropriate, to provide an overview of the study results. As appropriate, descriptive statistics will also be displayed by treatment group and by enrollment group. For categorical parameters, the number and percentage of subjects in each category will be presented in data summaries. The denominators for percentages will be based on the number of subjects (n) appropriate for analysis. Continuous variables will generally be summarized based on the following: n, mean, standard deviation, median, minimum, maximum, and standard error of the mean. Categorical data will be summarized using frequency tabulations (number and percentage of subjects).

Demographics and Baseline characteristics (medical histories, physical examinations, and concomitant medications) will be summarized using descriptive statistics for continuous variables and frequency distributions for discrete variables. Study subjects who discontinue the study along with reasons for discontinuation will be summarized and listed. Confidence intervals will be at the 90% and 95% levels. All statistical analyses will be performed using SAS v9.4.

13.2. Efficacy Analysis

13.2.1 Primary Efficacy Endpoint

The primary efficacy endpoint is the proportion of subjects experiencing either a histological improvement at Week 52 in NAS (i.e., ≥ 2 -point improvement in NAS with 1-point improvement in ballooning or inflammation) and without worsening of fibrosis score (by NASH CRN fibrosis score), **OR** resolution of steatohepatitis and no worsening of liver fibrosis (by NASH CRN fibrosis score). Resolution of steatohepatitis is defined as absence of fatty liver disease or isolated or simple steatosis without steatohepatitis and a NAS of 0 or 1 for inflammation, 0 for ballooning, and any value for steatosis.

Subjects will be eligible for analysis of the primary efficacy endpoint if they have completed at least 42 weeks of treatment and have a posttreatment biopsy.

The principal analysis of the primary efficacy endpoint will be based on the Intention-to-Treat (ITT) analysis set (Section 13.4.2). The treatment groups will be compared based on the primary efficacy endpoint using a one-sided Cochran-Mantel-Haenszel (CMH) test stratified by the randomization stratifications T2DM status (yes or no), region (North America or not North

America), and amount of fibrosis (F2 or F3) at the 0.05 significance level (where a higher responder proportion is a better outcome). A Clopper-Pearson 90% and 95% CI will be derived, and the odds ratio (with its 90% and 95% CI, using the control group as a reference group) will be produced to assess the treatment effect magnitude.

Evaluation of the robustness of the principal analysis of the primary efficacy endpoint will be carried out using a logistic regression with response as a dependent variable; treatment group, randomization stratification factors (T2DM status [yes or no], region [North America or not North America], and amount of fibrosis [F2 or F3]) as independent factors; and age as a baseline covariate. Other baseline covariates and other adjustment factors will be prespecified in the statistical analysis plan (SAP). The analysis of the primary efficacy endpoint will be repeated for the modified Intention-to-Treat (mITT) population (Section 13.4.2) to ascertain any changes in the conclusion of the principal analysis findings.

Subgroup analyses of the primary efficacy endpoint will be performed to assess whether the treatment effect is concordant among subgroups. The planned subgroup analyses are based on age category (<40 years, 40 to <65 years, and ≥ 65 years) and race (White, Black, Asian, and other).

A subject who discontinues treatment prior to Week 42, does not provide a histological assessment on or after Week 42, or who otherwise has missing data will be considered a non-responder.

Further sensitivity analysis of the primary efficacy endpoint will employ multiple imputations for binary data. Pertinent details are included in the SAP.

13.2.2 Secondary Efficacy Endpoints

The secondary efficacy endpoints for this study are:

- Proportion of MRI-PDFF $\geq 30\%$ responders at Week 26, where an MRI-PDFF $\geq 30\%$ responder is defined as a subject with $\geq 8\%$ liver fat content at Baseline who achieves a percent change (relative reduction) from Baseline in MRI-PDFF $\geq 30\%$. Treatment groups will be compared based on this secondary efficacy endpoint using an analysis similar to the primary efficacy endpoint.
- Proportion of MRI-PDFF $\geq 30\%$ responders at Week 52. Treatment groups will be compared based on this secondary efficacy endpoint using an analysis similar to the primary efficacy endpoint.
- Proportion of subjects with improvement in liver fibrosis ≥ 1 stage by NASH CRN fibrosis score without worsening of steatohepatitis (defined as no increase in NAS for ballooning, inflammation, or steatosis) at 52 weeks. Treatment groups will be compared based on this secondary efficacy endpoint using an analysis similar to the primary efficacy endpoint.
- Proportion of subjects with improvement in liver fibrosis ≥ 1 stage by NASH CRN score with no increase in any component of NAS at Week 52. Treatment groups will be compared based on this secondary efficacy endpoint using an analysis similar to the primary efficacy endpoint.

- Proportion of subjects with improvement in liver fibrosis ≥ 1 stage by NASH CRN score without increase of total NAS score at Week 52. Treatment groups will be compared based on this secondary efficacy endpoint using an analysis similar to the primary efficacy endpoint.
- Proportion of subjects with improvement in liver fibrosis ≥ 1 stage by NASH CRN score without any worsening of NASH (defined as no worsening of ballooning and lobular inflammation; a 1 grade change in steatosis may be acceptable) at Week 52. Treatment groups will be compared based on this secondary efficacy endpoint using an analysis similar to the primary efficacy endpoint.
- Proportion of subjects experiencing **both** of the following at Week 52:
 - Resolution of steatohepatitis on overall histopathological reading and no worsening of liver fibrosis on NASH CRN fibrosis score. Resolution of steatohepatitis is defined as absent fatty liver disease or isolated or simple steatosis without steatohepatitis and a NAS score of 0-1 for inflammation, 0 for ballooning, and any value for steatosis

AND

- Improvement in liver fibrosis greater than or equal to one stage (NASH CRN fibrosis score) and no worsening of steatohepatitis (defined as no increase in NAS for ballooning, inflammation, or steatosis).

Treatment groups will be compared based on this secondary efficacy endpoint using an analysis similar to the primary efficacy endpoint.

- Proportion of subjects experiencing **both** of the following at Week 52:
 - Histological improvement at Week 52 in nonalcoholic fatty liver disease (NAFLD) activity score (NAS) (i.e., ≥ 2 points improvement in NAS with ≥ 1 point improvement in ballooning or inflammation) and without worsening of fibrosis (by NASH Clinical Research Network [CRN] fibrosis score)

AND

- Improvement in liver fibrosis greater than or equal to one stage (NASH CRN fibrosis score) and no worsening of steatohepatitis (defined as no increase in NAS for ballooning, inflammation, or steatosis).

Treatment groups will be compared based on this secondary efficacy endpoint using an analysis similar to the primary efficacy endpoint.

- Proportion of subjects experiencing **both** of the following at Week 52:
 - Resolution of steatohepatitis and no worsening of liver fibrosis (by NASH CRN fibrosis score). Resolution of steatohepatitis is defined as absence of fatty liver disease or isolated or simple steatosis without steatohepatitis and a NAS of 0 or 1 for inflammation, 0 for ballooning, and any value for steatosis.

AND

- Histological improvement at in NAS (≥ 2 points improvement in NAS).

Treatment groups will be compared based on this secondary efficacy endpoint using

an analysis similar to the primary efficacy endpoint.

[figure not shown]
- Proportion of subjects with histological improvement at Week 52 in NAS. Treatment groups will be compared based on this secondary efficacy endpoint using an analysis similar to the primary efficacy endpoint.
- MRI-PDFF percent change and change from Baseline at Week 26. This secondary efficacy endpoint will be compared between treatment groups using a one-sided Wilcoxon rank-sum test. An analysis of covariance (ANCOVA) model will also be used with percent change and change from baseline as the dependent variable; treatment group, T2DM status (yes, no), region (North America, not North America), and amount of fibrosis (F2, F3) as factors; and Baseline as a covariate. Least-squares (LS) means and their differences will be estimated from the ANCOVA model and their corresponding 95% CI will be derived. Inferential statistics will be presented for both the ANCOVA model and the Wilcoxon test. For the continuous secondary endpoints with sufficient postbaseline frequency of measurements, a mixed model repeated measure (MMRM) model will also be employed.
- MRI-PDFF percent change and change from Baseline at Week 52. This secondary endpoint will be analyzed similarly to MRI-PDFF percent change and change from Baseline at Week 26, as described above.
- Proportion of subjects with NASH resolution at 52 weeks. Treatment groups will be compared based on this secondary efficacy endpoint using an analysis similar to the primary efficacy endpoint.
- Change from Baseline in ALT, AST, and GGT at Weeks 26 and 52 and at each study visit. This secondary endpoint will be analyzed similarly to MRI-PDFF percent change and change from Baseline at Week 26, as described above.
- Change from Baseline in LDL-C and other lipid levels at Weeks 26 and 52 and at each study visit. This secondary endpoint will be analyzed similarly to MRI-PDFF percent change and change from Baseline at Week 26, as described above.
- Change from Baseline in collagen/fibrous area and fibrosis score, assessed by digital pathology, at Week 52. This secondary endpoint will be analyzed similarly to MRI-PDFF percent change and change from Baseline at Week 26, as described above.
- Changes from Baseline in metabolic parameters, including fasting insulin, fasting glucose, HOMA-IR, adipo-IR, and HbA1c levels at Weeks 26 and 52 and at each study visit. This secondary endpoint will be analyzed similarly to MRI-PDFF percent change and change from Baseline at Week 26, as described above.
- Change from Baseline in FGF-21, adiponectin, and other NASH biomarker levels at Weeks 26 and 52 and at each study visit. This secondary endpoint will be analyzed similarly to MRI-PDFF percent change and change from Baseline at Week 26, as described above.
- Change from Baseline in FibroScan and CAP score results at Weeks 26 and 52. This secondary endpoint will be analyzed similarly to MRI-PDFF percent change and change from Baseline at Week 26, as described above.

- Change from Baseline in PRO-C3 and other fibrosis biomarkers at Weeks 4, 13, 26, and 52. This secondary endpoint will be analyzed similarly to MRI-PDFF percent change and change from Baseline at Week 26, as described above.
- Change from Baseline in ELF score at Weeks 26 and 52. This secondary endpoint will be analyzed similarly to MRI-PDFF percent change and change from Baseline at Week 26, as described above.

The analysis of the primary and secondary endpoints will be carried out for the ITT analysis set and repeated for the mITT analysis set.

13.2.3. Exploratory Endpoints

Exploratory endpoints will be summarized primarily with descriptive statistics. Select endpoints may be evaluated with statistical tests and/or CIs. Further details on exploratory analyses will be provided in the SAP.

13.3. Safety Analysis

Safety data will be evaluated for the Safety population (Section 13.4.2) on the basis of TEAEs, clinical laboratory assessments, vital signs, ECGs, weight, and physical examinations. Changes from Baseline in key clinical laboratory measurements, vital signs, physical examinations, and weight will be summarized by treatment group using standard descriptive statistics. A TEAE is defined as an AE that was not present prior to treatment with study drug but appeared following treatment or was present at treatment initiation but worsened during treatment. All AEs will be coded by preferred term using the Medical Dictionary for Regulatory Activities (MedDRA; current version) and NCI CTCAE (current version) grading.

TEAE incidence rates will be summarized using frequency and percentage for each treatment group and in total. TEAEs through 30 days after the last dose of study treatment will be

summarized by MedDRA (current version) system organ class and preferred term. AEs will also be summarized by NCI CTCAE grade and by causality (attribution to study treatment, related/not related to investigational medicinal product). Grades 3 and 4 AEs, SAEs, and AEs resulting in dose modification or treatment discontinuation will be summarized by preferred terms. Investigational medicinal product compliance and tolerability ratings will be summarized descriptively for each treatment group.

All safety data will be presented in data listings.

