5.2. TVB-2640

Sagimet Biosciences has developed an oral (PO), once-daily (QD) FASN inhibitor, TVB-2640. This drug has been evaluated in >300 humans to date, including patients with NASH, patients with solid tumors, and healthy adults, some of whom had characteristics of the metabolic syndrome. The safety, pharmacokinetic (PK), and pharmacodynamic (PD) parameters of TVB-2640 have been measured.

Safety data are available from 129 subjects with NASH who have been enrolled in the US and China in Study CLIN-005 (FASCINATE-1). In the US, subjects received 25 mg TVB-2640, 50 mg TVB-2640, or placebo PO, QD for approximately 12 weeks. A total of 68 subjects were treated with TVB-2640. Overall, 62 (63%) subjects experienced at least 1 treatment-emergent adverse event (TEAE), all of which were assessed by the Investigator as mild, with the exception of 1 case each of Grade 2 urinary tract infection and Grade 2 increased appetite at 25 mg and Grade 2 dyspnea at 50 mg, all of which resolved without dose adjustment. No on-treatment serious adverse events (SAEs) occurred in either TVB-2640 dose group. Overall, the most common TEAEs among TVB-2640-treated subjects were headache (6 subjects; 9%) and peripheral edema, rash, and upper respiratory tract infection (4 subjects each; 6%). Two (3%) subjects discontinued TVB-2640 due to a TEAE: 1 subject due to mild eye allergy (after 1 day of dosing) and the other due to mild conjunctivitis; both of these events occurred in the 25-mg dose group.

Among the 30 subjects enrolled in China, 21 were treated with TVB-2640 50 mg and 9 were treated with placebo for 12 weeks. Seventeen (81.0%) patients experienced at least 1 TEAE, all of which were reported as Grade 2 or less, with the exception of 2 cases of Grade 3 hypertriglyceridemia, both of which were deemed as unrelated to TVB-2640. All TEAEs resolved without dose adjustment. No on-treatment SAEs occurred. Skin and subcutaneous tissue disorders were the most common type of TEAEs. Overall, the most common TEAEs among TVB-2640-treated patients were dry eye (8 patients), skin exfoliation (7 patients), and palmar-plantar erythrodysesthesia syndrome (PPE) and upper respiratory tract infection (each 3 patients).

TVB-2640 reduced hepatic DNL in subjects with features of metabolic syndrome ([Syed-Abdul, 2020](#)). Reduction of DNL was dose dependent. The lowest dose tested, 50 mg, exhibited a

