8.3. Subject Withdrawal Criteria

Subjects will be informed that they have the right to withdraw from the study at any time for any reason, without prejudice to their medical care. Study drug must be permanently discontinued and the subject withdrawn from the study for any of the following TEAEs, with the subject managed as indicated:

- **Palmar-plantar Erythrodysesthesia (PPE):** For mild to moderate symptoms of PPE (e.g., redness, pain, or scaling of hands or feet), study drug should be interrupted and symptomatic measures, including hand cream such as “Udder Cream,” instituted immediately. Study drug may be resumed after resolution of symptoms; study drug should be discontinued permanently if PPE Grade ≥ 2 recurs after study drug is resumed. Study drug should also be permanently discontinued at the first sign of significant/severe, redness, pain, or scaling of hands or feet, and symptomatic measures instituted immediately.
- **Dyspnea or suspected pneumonitis:** Study drug should be permanently discontinued for subjects with shortness of breath or other respiratory symptoms that are otherwise unexplained. An unscheduled SARS-CoV-2 test should be done if a subject develops dyspnea or pneumonitis. The subject is to be carefully monitored for improvement. In the event that symptoms worsen or present as more than mild intensity, immediate referral to a qualified pulmonologist for definitive diagnosis and treatment should be undertaken.
- **Visual symptoms (including keratitis):** Study drug should be permanently discontinued at the first sign of significant redness (erythema), pain, or dryness affecting one or both eyes. Symptomatic measures, including moisturizing eye drops, should be instituted. In the event that symptoms worsen or present as more than mild, immediate referral to a qualified ophthalmologist or optometrist should be undertaken.

- **Suspected drug-induced liver injury (DILI):** Study drug intake should be managed according to the different laboratory and clinical circumstances itemized in [Appendix A](#) for subjects with suspected DILI.

Refer to the Study Manual for additional details regarding the assessment and management of these events.

Furthermore, the Investigator also has the right to withdraw subjects from the study for any of the following reasons:

- Progression of underlying disease that, in the opinion of the Investigator, precludes further study treatment.
- Occurrence of any other unacceptable AE.

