12.2.3. Recording Adverse Events

Each subject must be carefully monitored for the development of any AEs. This information should be obtained in the form of non-leading questions (e.g., “How are you feeling?”) and from signs and symptoms detected during each physical examination, observations on the part of study personnel, and spontaneous reports from subjects.

All AEs (serious and non-serious) spontaneously reported by the subject and/or in response to an open question from study personnel or revealed by observation, physical examination, or other diagnostic procedures will be documented in the subject’s source documents and recorded in the eCRF. Any clinically relevant (as determined by the Investigator) deterioration in laboratory assessments or other clinical findings is considered an AE and must be recorded in the subject’s source documents and in the eCRF.

Information about AEs will be collected from Screening (i.e., after the ICF is signed) through 28 days after the last dose of study drug. The AE term should be recorded in standard medical terminology when possible. Also, when possible, signs and symptoms indicating a common underlying pathology should be noted as one comprehensive event. For each AE, the Investigator will evaluate and report the onset date, resolution date, intensity, causality, action taken, serious outcome (if applicable), and whether or not it caused the subject to discontinue the study.

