12.2.4. Reporting Serious Adverse Events

All SAEs (related and unrelated) occurring from Screening through 28 days after the last study drug dose are to be reported within 24 hours of first awareness on the part of site staff. Any suspected case of pneumonitis considered an adverse events of special interest, should be reported in the same manner as an SAE.

The Investigator must report all SAEs within 24 hours of discovery via the EDC system, which will trigger email notifications to the Syneos Health, Medical Monitor/Safety team. In the event the EDC system is not available, then SAE reports must be emailed [REDACTED]:

[REDACTED]

Alternatively, a pdf copy of the SAE report form may be faxed [REDACTED]

The Investigator must complete and electronically sign and date the SAE pages of the eCRF and verify the accuracy of the information recorded on the SAE pages with the corresponding source documents.

Additional follow-up information, if required or available, should be submitted within the EDC system within 1 business day of receipt and this should be completed on a follow-up SAE form and placed with the original SAE information and kept with the appropriate section of the eCRF and/or study file.

Sagimet Biosciences is responsible for notifying the relevant regulatory authorities of certain events. It is the Investigator's responsibility to notify the Institutional Review Board (IRB) or Independent Ethics Committee (IEC) of all SAEs that occur at his or her study center.

Investigators will also be notified of all unexpected, serious, drug-related events (i.e., all 7- or 15-Day Safety Reports) that occur during the clinical study. Each study center is responsible for notifying its IRB/IEC of these additional SAEs.

Any incident diagnosis of cancer that occurs in a subject taking part in the study, from the time written informed consent is provided until study completion/exit, must be reported as an SAE ('medically important') within 24 hours of first awareness on the part of site staff.

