10. SAFETY

Safety will be evaluated based on data collected for adverse events, vital signs, physical examinations, electrocardiogram (ECG), ophthalmologic examinations, and laboratory data. No formal statistical testing will be conducted for the safety analyses. Descriptive statistics will be used to evaluate safety data in this study. Summaries will be presented by treatment group.

All safety analysis reporting will be based on the Safety population. All safety data will be listed by treatment group and subject.

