An overview of TEAEs will be produced, including counts and percentages of subjects with any incidences of: TEAEs, TEAEs related to study treatment, serious adverse events (SAEs), TEAEs leading to study drug discontinuation, TEAEs with CTCAE grade 3 or higher, and fatal SAEs. The number of AEs will also be included in the summary.

In addition to the overview of TEAEs, the following summaries of AEs will be provided for the safety population by treatment group and overall:

- TEAEs by SOC and PT
- TEAEs related to study treatment by SOC and PT
- CTCAE Grade 3 or higher TEAEs by SOC and PT
- CTCAE Grade 3 or higher TEAEs related to study treatment by SOC and PT
- SAEs by SOC and PT
- TEAEs leading to treatment discontinuation by SOC and PT
- Skin and subcutaneous tissue disorders TEAEs by PT
- Eye disorder TEAEs by PT

Summaries of TEAEs by SOC, PT, and maximum severity as well as TEAEs by SOC, PT, and maximum relationship to study treatment will also be prepared.

Skin and subcutaneous tissue disorders and eye disorder TEAE summaries will also be performed for the mITT population.

A comprehensive listing of all AEs will be provided in a by-subject data listing. In addition, the following listings will be provided:

- TEAEs related to study treatment
- SAEs
- TEAEs leading to treatment discontinuation; and
- Fatal AEs.

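### Crude TEAE percentages do not account for unequal follow-up; if TVB-2640 subjects stop earlier than placebo subjects, risks of their other TEAEs would be understated

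*Protocol*

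**What the plan says.** **Summary measure.** Protocol 13.3: "TEAE incidence rates will be summarized using frequency and percentage for each treatment group and in total". SAP 10.1 plans an overview "including counts and percentages of subjects with any incidences of" the listed TEAE categories, adds the number of AEs, and then gives tables by system organ class and preferred term. SAP Section 10 adds: "No formal statistical testing will be conducted for the safety analyses". Duration of exposure is summarized separately (SAP 8.7) and is not used as a denominator for any AE table.

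**Observation window.** Protocol 12.2.3 collects AEs "through 28 days after the last dose of study drug", and Protocol 12.2.4 reports SAEs "occurring from Screening through 28 days after the last study drug dose". Protocol 13.3 uses a different window: "TEAEs through 30 days after the last dose of study treatment will be" summarized. The TEAE definition in SAP 10.1 covers any AE after the first dose and states no end.

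**Denominator.** The Safety population is every randomized subject with at least one dose (Protocol 13.4.2.3, SAP Section 6), however long treatment lasted.

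**Stopping.** Protocol 8.3 opens: "Study drug must be permanently discontinued and the subject withdrawn from the study for any of the following TEAEs". The list is palmar-plantar erythrodysesthesia (PPE), dyspnea or suspected pneumonitis, visual symptoms and suspected drug-induced liver injury. The PPE entry lets mild to moderate cases interrupt and resume, and Appendix A keeps subjects whose drug is discontinued for liver findings under study follow-up.

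**The concern.** A percentage of subjects with an event compares two arms fairly only if both are observed for about the same time. Here the observation time depends on treatment: stopping drug closes AE collection four weeks later, while the subject still counts in the denominator as if observed to about Week 56.

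Some of the stopping criteria concern suspected drug effects. In the Phase 2a study (Protocol 5.2), the 21 subjects in China on 50 mg had dry eye in 8, skin exfoliation in 7 and PPE in 3. More early stopping on TVB-2640 is therefore a reasonable possibility. If it happens, the percentages for hepatic, respiratory, metabolic, infectious, serious and Grade 3 or higher events would be lowered on TVB-2640, and more so the worse the drug is tolerated.

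Safety and tolerability is a primary objective (Protocol 6.1.1), and the by-arm percentages are what readers will compare, with or without a test.

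**Working it through.** **The plan's own figures.** The documents state no AE rate and no expected exposure for this trial. The only related figure is the 18.5% dropout behind N = 162 (Protocol 13.5), and it reproduces. With 40% vs 20%, one-sided 0.05, 80% power, 2:1 allocation and unpooled variance, placebo n = (1.645 + 0.842)² × (0.16 + 0.24/2)/0.2² = 43.3, so 44 + 88 = 132, and 132/0.815 = 161.96, rounded up to 162. The 18.5% is pooled (0.185 × 162, about 30 subjects), so it shows that follow-up will be cut short for some but not in which arm.

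**Main calculation.** All inputs here are assumptions: constant hazard L, the same in both arms; a fraction p stops at Week 13 and is observed to Week 17; everyone else is observed to Week 56; stopping is unrelated to the event studied.

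- Full-period risk 20%: L = −ln(0.80)/56 = 0.00398 per week. Risk by Week 17 = 1 − exp(−17L) = 0.0655.
- Crude risk = (1 − p) × 0.20 + p × 0.0655.
- Mean follow-up = 56(1 − p) + 17p weeks.

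| Stopping, TVB-2640 vs placebo | Mean follow-up (weeks) | Crude risk | Ratio | Hazard ratio that would look like no difference |
|---|---|---|---|---|
| 15% vs 5% | 50.2 vs 54.1 | 18.0% vs 19.3% | 0.93 | 1.08 |
| 25% vs 10% | 46.3 vs 52.1 | 16.6% vs 18.7% | 0.89 | 1.14 |
| 30% vs 10% | 44.3 vs 52.1 | 16.0% vs 18.7% | 0.86 | 1.19 |
| equal | equal | equal | 1.00 | 1.00 |

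For full-period risks of 5% to 40%, the ratio over the three unequal pairs runs from 0.85 to 0.93. If the 25% and 10% are swapped between arms, the ratio is 1/0.89 = 1.12.

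**Second model: stopping spread over the year.** Discontinuation is exponential to Week 52 at rate d, AE follow-up runs to last dose + 4 weeks, and P(no event) = exp(−4L) × [d/(d+L) × (1 − exp(−52(d+L))) + exp(−52(d+L))]. At 20% full-period risk and no true effect:

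| Stopping, TVB-2640 vs placebo | Crude risk | Ratio |
|---|---|---|
| 18.5% vs 18.5% | 18.3% vs 18.3% | 1.00 |
| 25% vs 18.5% | 17.7% vs 18.3% | 0.97 |
| 35% vs 18.5% | 16.7% vs 18.3% | 0.91 |
| 35% vs 10% | 16.7% vs 19.1% | 0.87 |
| 10% vs 18.5% | 19.1% vs 18.3% | 1.04 |

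**Which events are affected.** In a simulation with 18.5% background discontinuation and a 20%-risk event that itself stops treatment, first-event incidence of that trigger event is about 18.4% whether or not stopping follows. Incidence of a different AE falls from 18.4% to 16.9% when every trigger event stops treatment.

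**Does a person-time rate repair it?** Under constant hazard it does: the rate ratio is 1.00 in every row above. Now suppose instead that the whole 20% risk falls in Weeks 0 to 13, with stopping at Week 13 as in the main calculation. Crude percentages are then unbiased. Subjects with an event contribute 1.25 weeks to the mean time at risk (with λ = −ln(0.80)/13, 0.2/λ − 13 × 0.8). Mean time at risk = 1.25 + 0.8 × mean follow-up:

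- 25% vs 10%: 38.25 vs 42.93 weeks, false rate ratio 42.93/38.25 = 1.12.
- 15% vs 5%: 1.08. 30% vs 10%: 1.17.

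Cumulative incidence of first event, censored at the end of the window, returns 20% in both arms under either hazard shape, provided that stopping is unrelated to the event studied.

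**The case against.** The strongest objection is that no bias has been shown. A reader might infer that AE risks on TVB-2640 are understated, and the documents do not support that. They give no stopping rate by arm. The Phase 2a evidence in Protocol 5.2 also cuts the other way: the TEAEs in China resolved with no change of dose, and only 2 of 68 TVB-2640 subjects in the US stopped for a TEAE, both at 25 mg. Every stopping pair above is assumed. This stands, and it makes the point conditional. It does not remove it, because those data cover about 12 weeks and this trial runs for 52.

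A reader might also infer that skin and eye risks are the ones hidden. They are not: the event that stops treatment is counted when it occurs. Nor does every on-target event force a stop. Mild to moderate PPE may resume, Protocol 7.3 permits dose modification for some on-target events, and Appendix A includes interruption with possible restart.

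Unequal follow-up would also be visible. SAP 8.1 reports withdrawals, reasons and study duration by arm, and SAP 8.7 reports exposure. That helps a reader to suspect a problem but not to correct a given AE table.

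Finally, the effect is modest. In the 25% vs 10% case it is about 2 of 108 subjects (108 × 0.020 = 2.2). At 20% risk in both arms, the 95% interval for a risk ratio with 108 vs 54 is about 0.52 to 1.92: the standard error of its log is √(0.8/21.6 + 0.8/10.8) = 0.33. This stands as a reason for proportion. The shift is still systematic, and it would apply to all the other TEAE tables together.

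**Conclusion.** The gap is real: crude percentages only, AE observation tied to the last dose, and nothing that adjusts for time at risk. Its consequence is conditional. If TVB-2640 subjects stop earlier, TEAEs other than the trigger are understated, with a crude ratio of about 0.85 to 0.93 over stopping pairs from 15% vs 5% to 30% vs 10%. With equal stopping there is no bias, and with more stopping on placebo it runs the other way (1.04 at 10% vs 18.5% in the second model). The sizes rest on assumed stopping fractions, constant hazards, and stopping unrelated to the event studied.

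The direction cannot be known in advance, so the adjusted display should be specified before unblinding. This is an inexpensive improvement bearing on a primary safety objective, not a demonstrated error in the safety conclusion.

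Two inconsistencies belong to the same point, because they set the time at risk: the three AE windows (28 days, 30 days, open-ended), and withdrawal from the study in Protocol 8.3 against continued follow-up after discontinuation in Appendix A.

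**What to change.** In Protocol 13.3 and SAP 10.1:

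- Keep n (%) as planned.
- Add, in the Safety population by arm, cumulative incidence of first event from first dose, censored at the end of the AE window, with the arm difference and 95% CI. Do this for any TEAE, related TEAE, Grade 3 or higher, SAE, and the skin, eye, respiratory and hepatobiliary groups. State that censoring at stopping assumes stopping is unrelated to the event studied.
- Add exposure-adjusted first-event rates per 100 subject-years as a supplement. State that they assume a roughly constant hazard and can err the other way when events cluster early (false ratios of 1.08 to 1.17 in the early-event check above).
- Do not rely on the mITT skin and eye summaries in SAP 10.1 as the additional view. mITT requires at least 42 weeks of treatment, so it leaves out subjects stopped before then for those very events.
- Reconcile the 28-day collection window (Protocol 12.2.3), the 30-day summary window (Protocol 13.3) and the SAP TEAE definition, and use the same end of window for the censoring time.
- Reconcile Protocol 8.3 with Appendix A on whether a subject who stops drug remains under follow-up. Which rule applies is for the sponsor to settle; the analysis needs a single stated rule.

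The cost is a few extra tables and figures from data already collected.
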